5.4.6. Procedure for Subjects Exhibiting Serotonin Syndrome

As noted in Section 1.2.1, there is a risk that epacadostat may cause an increase in serotonin levels in the brain that might trigger SS (Boyer and Shannon 2005) when administered in combination with other serotonergic agents. This syndrome has been most closely associated with use of MAOIs, meperidine, linezolid, or methylene blue; all of these agents are prohibited during the study. Selective serotonin reuptake inhibitors and SNRIs are permitted in the study. Serotonin syndrome usually manifests with autonomic changes, mental status changes, and neurological findings. These mild, moderate, and severe signs and symptoms of SS (summarized in Table 17) should be evaluated in the context of possible comorbid conditions as well.

The following procedures will be implemented if subjects exhibit the signs/symptoms of SS described in Table 17, including tremor; hyperreflexia; and spontaneous, ocular, or inducible clonus, together with agitation, fever, diaphoresis, or muscle rigidity:

- Immediately interrupt all treatment administration.
- Immediately interrupt any SSRI or SNRI administration.
- Provide appropriate medical management of the subject until all signs/symptoms are resolved (eg, IV fluids and/or sympathomimetic amines for hypotension, benzodiazepines for agitation, administration of 5-hydroxytryptamine antagonists, such as cyproheptadine).
- If etiologies other than SS are excluded, nivolumab and ipilimumab administration may be resumed unless other AE management guidelines apply for the specific event.
- If subject chooses to withdraw from the study or must restart treatment with SSRI or SNRI, the subject should be scheduled for a follow-up visit. Treatment with SSRI or SNRI may be initiated 2 weeks after resolution of signs and symptoms of SS.
- If a subject had experienced moderate or severe unconfounded SS in the opinion of the investigator, without concomitant SSRI or SNRI use, or serotonergic concomitant medications, only nivolumab/ipilimumab administration may be resumed; epacadostat treatment should be permanently discontinued.

Table 17: Sign and Symptoms of Serotonin Syndrome

Seriousness	Autonomic Signs	Neurological Signs	Mental Status	Other
Mild	Afebrile or low-grade fever Tachycardia Mydriasis Diaphoresis or shivering	Intermittent tremor Akathisia Myoclonus Mild hyperreflexia	Restlessness Anxiety	
Moderate	Increased tachycardia Fever (up to 41°C) Diarrhea with hyperactive bowel sounds Diaphoresis with normal skin color	Hyperreflexia Inducible clonus Ocular clonus (slow continuous lateral eye movements) Myoclonus	Easily startled Increased confusion Agitation and hypervigilance	Rhabdomyolysis Metabolic acidosis Renal failure Disseminated intravascular coagulopathy (secondary to hyperthermia)
Severe	Temperature often more than 41°C (Secondary to increased tone)	Increased muscle tone (lower limb > upper) Spontaneous clonus Substantial myoclonus or hyperreflexia	Delirium Coma	As above

Source: [Boyer and Shannon 2005](#).

5.4.7. Management of Infusion Reactions

Table 18 shows treatment guidelines for subjects who experience an infusion reaction associated with administration of nivolumab, ipilimumab, or lirilumab. Signs and symptoms usually develop during or shortly after drug infusion and generally resolve completely within 24 hours of completion of infusion.

Table 18: Infusion Reaction Treatment Guidelines

CTCAE Grade	Treatment	Premedication at Subsequent Dose Administration
Grade 1: Mild reaction; infusion interruption not indicated; intervention not indicated.	Increase monitoring of vital signs as medically indicated until the subject is deemed medically stable, in the opinion of the investigator.	None.
Grade 2: Requires infusion interruption but responds promptly to symptomatic treatment (eg, antihistamines, NSAIDs, narcotics, IV fluids); prophylactic medications indicated for ≤ 24 hours.	
Stop infusion and monitor symptoms. Additional appropriate medical therapy may include, but is not limited to, the following:
 
 • IV fluids • Antihistamines • NSAIDs • Acetaminophen • Narcotics 
Increase monitoring of vital signs as medically indicated until the subject is deemed medically stable in the opinion of the investigator.
 
If symptoms resolve within 1 hour of stopping drug infusion, the infusion may be restarted at 50% of the original infusion rate. Otherwise, dose administration will be held until symptoms resolve, and the subject should be premedicated for the next scheduled dose.
 
Subjects who develop Grade 2 toxicity despite adequate premedication should be permanently discontinued from further study treatment.
	
Subject may be premedicated 1.5 h (± 30 min) before infusion with the following:
 
 • Diphenhydramine 50 mg orally (or equivalent dose of antihistamine). • Acetaminophen 500-1000 mg orally (or equivalent dose of antipyretic).
Grade 3: Prolonged (ie, not rapidly responsive to symptomatic medication and/or brief interruption of infusion); recurrence of symptoms following initial improvement; hospitalization indicated for other clinical sequelae (eg, renal impairment, pulmonary infiltrates).	
Stop infusion. Additional appropriate medical therapy may include, but is not limited to, the following:
 
 • IV fluids • Antihistamines • NSAIDs • Acetaminophen • Narcotics • Oxygen • Pressors • Corticosteroids 	No subsequent dose.
Grade 4: Life-threatening; pressor or ventilatory support indicated.	
 • Epinephrine 
Increase monitoring of vital signs as medically indicated until the subject is deemed medically stable, in the opinion of the investigator.
 
Hospitalization may be indicated.
 
Subject is permanently discontinued from further study treatment.
	

Note: Appropriate resuscitation equipment should be available in the room and a physician readily available during the period of drug administration.

5.4.8. Criteria for Permanent Discontinuation of Study Treatment

The occurrence of unacceptable toxicity not caused by the underlying malignancy will be presumed to be related to study treatment and will require that the study drug be permanently discontinued. Unacceptable toxicity is defined as follows:

- Grade 4 or life-threatening AEs, except with approval from the medical monitor.
- Toxicity requiring more than 2 dose reductions of epacadostat, or dose reductions below 25 mg BID.
- \geq Grade 2 ocular irAE.
- Occurrence of an AE that is related to treatment with the study drug that, in the judgment of the investigator or the sponsor's medical monitor, compromises the subject's ability to continue study-specific procedures or is considered to not be in the subject's best interest.
- Persistent AE requiring a delay of therapy for more than 4 weeks (28 days) unless a greater delay has been approved by the sponsor.

5.5. Withdrawal of Subjects From Study Treatment

5.5.1. Withdrawal Criteria

Subjects may withdraw consent at any time for any reason or be withdrawn from study treatment at the discretion of the investigator should any untoward effect occur. In addition, a subject may be withdrawn by the investigator or the sponsor if enrollment in the study is inappropriate, the study plan is violated, or for administrative and/or other safety reasons.

Subjects **must** be withdrawn from study treatment for the following reasons:

- The subject becomes pregnant.
- Consent is withdrawn. Subjects may choose to withdraw from the study at any time without penalty of jeopardizing their health care or loss of benefits to which the subject is otherwise entitled.
Note: Consent withdrawn means that the subject can no longer be followed and no additional data can be collected.
- Further participation would be injurious to the subject's health or well-being, in the investigator's medical judgment.
- Unacceptable toxicity (see Section 5.4.8). Subjects with unacceptable toxicities must be withdrawn from study treatment but will continue in the safety follow-up period of the study (see Section 6.4).
- The subject has received study treatment for 2 years (ie, 24 months have elapsed since Cycle 1 Day 1).
- The study is terminated by the sponsor.
- The study is terminated by the local health authority, IRB, or IEC.

A subject **may** be discontinued from study treatment as follows:

- Radiographic progression of disease per RECIST v1.1 (see [Appendix E](#)). A subject may continue on treatment after radiographic progression is confirmed per RECIST v1.1 if clinically stable or clinically improved, pending confirmation of disease progression [REDACTED] (see Sections [5.5.1.1](#) and [7.6.1](#)).
- If, during the course of the study, a subject is found not to have met eligibility criteria (see Section [3](#)), the medical monitor, in collaboration with the investigator, will determine whether the subject should be withdrawn from the study.
- If a subject is lost to follow-up or noncompliant with study procedures or study treatment in the investigator's opinion, the sponsor should be consulted for instruction on handling the subject.

5.5.1.1. Treatment After Initial Evidence of Radiologic Evidence of Disease Progression

Immunotherapeutic agents may produce antitumor effects by potentiating endogenous cancer-specific immune responses. The response patterns seen with such an approach may extend beyond the typical time course of responses seen with cytotoxic agents and can manifest as a clinical response after an initial increase in tumor burden or the appearance of new lesions.

[REDACTED]

[REDACTED]

[REDACTED]

Subjects may receive study treatment pending confirmation of PD if they are clinically stable as defined by the following criteria:

- Absence of clinically significant signs and symptoms (including worsening of laboratory values) indicating disease progression.
- No decline in ECOG performance status.
- No requirement for intensified management of disease-related symptoms.
- Absence of rapid progression of disease.
- Absence of progressive tumor at critical anatomical sites (eg, spinal cord compression) requiring urgent alternative medical intervention.

Subjects who are clinically unstable are not required to have repeat imaging for the confirmation of PD.

If a follow-up scan was not performed after unconfirmed PD (eg, due to patient refusal or patient death), the initial date of unconfirmed progression will be considered the date of PD.

Table 19: Imaging and Treatment After First Radiologic Evidence of Progressive Disease

	Clinically Stable		Clinically Unstable	
	Imaging	Treatment	Imaging	Treatment
Initial unconfirmed progressive disease (iUPD) OR subsequent iUPD after iSD, iPR or iCR.	Repeat imaging at ≥ 4 and ≤ 8 weeks to confirm PD.	May continue study treatment at the investigator's discretion while awaiting confirmatory scan.	Repeat imaging at ≥ 4 weeks to confirm PD if possible.	Discontinue treatment.
Next evaluable scan confirms PD (iCPD).	No additional imaging required.	Discontinue treatment.	No additional imaging required.	N/A
Repeat scan shows iUPD, iSD, iPR, or iCR. ^a	Continue regularly scheduled imaging assessments at 8 and 16 weeks after the start of treatment and then every 12 weeks (± 7 days) thereafter.	Continue study treatment at the investigator's discretion.	Continue regularly scheduled imaging assessments at 8 and 16 weeks after the start of treatment and then every 12 weeks (± 7 days) thereafter.	May restart study treatment if condition has improved and/or is clinically stable per investigator's discretion.

^a iSD, iPR, and iCR is based on baseline or nadir.

In determining whether the tumor burden has increased or decreased, investigators should consider all baseline and any new target lesions as well as baseline and any new nontarget lesions.

Progressive disease (iCPD) is confirmed if further increase in tumor burden, compared to the last assessment, is seen as evidenced by one or more of the following:

- Continued increase in tumor burden (from iUPD) where RECIST 1.1 definitions of progression had been met (from nadir) in target, nontarget disease or new lesions
 - Progression in target disease worsens with an increase of at least 5 mm in the absolute value of the sum;
 - Continued unequivocal progression in nontarget disease with an increase in tumor burden;
 - Increase in size of previously identified new lesion(s) (an increase of at least 5 mm in the absolute value of the sum of those considered to be target new lesions) or additional new lesions
- RECIST v1.1 criteria are met in lesions types (target or nontarget or new lesions) where progression was not previously identified, including the appearance of additional new lesions.

If iUPD is not confirmed at the next assessment, then the appropriate response will be assigned (iUPD if the criteria are still met, but no worsening, or iSD, iPR, or iCR if those criteria are met compared to baseline). As can be seen in [Table 19](#), the prior documentation of iUPD does not preclude assigning iCR, iPR, or iSD in subsequent time-point assessments or as best overall response providing that iCPD is not documented at the next assessment after iUPD.

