Lirilumab will be administered as a 240 mg IV infusion over 60 minutes (\pm 5 minutes) on Day 1 of Cycle 1 and then Day 1 of every other cycle thereafter (ie, Cycle 3, Cycle 5, etc). Lirilumab will be administered after nivolumab on visit days when both agents are given. Intrasubject dose escalation of lirilumab is not allowed.

Treatment Cycles and Duration of Treatment:

Study treatment will be administered in continuous 14-day cycles. Subjects will continue to receive study treatment for up to 2 years as long as the subject is deriving benefit and has not met any of the Protocol-defined conditions for treatment discontinuation. Intrasubject dose-escalation is not permitted.

Study Schedule/Procedures:

The study comprises the following parts:

- **Screening:** Up to 28 days before enrollment. Screening will begin at the time that the subject signs the informed consent and will continue until the date the subject is enrolled in the study (Cycle 1 Day 1).
- **Treatment:** Treatment cycles will be 14 days in length. Subjects will have regularly scheduled study visits on Day 1 (± 3 days) of each cycle. Clinic visits will also occur on Day 8 (± 1 day) during the first 3 cycles.
- **End of treatment:** + 7 days after withdrawal from study treatment.
- **Safety follow-up:** 30 days (+ 7 days), 100 days (± 7 days), and 150 days (± 7 days; Treatment Group B only) after the last dose of study treatment.

Safety Assessments:

Subjects will have regularly scheduled study visits at the clinical site on Day 1 of every cycle where targeted physical examinations, vital sign collection, collection of concomitant medications, and AE assessments will be performed. Twelve-lead ECGs will be performed at screening, Cycle 1 Day 1, Cycle 2 Day 1, and at the end-of-treatment visit. Laboratory assessments will be collected during each treatment cycle. Toxicities will be monitored continuously and will be graded using the National Cancer Institute's CTCAE v4.03 criteria.

Regular telephone conferences with study investigators will be scheduled by the sponsor in order to review cohort-specific data and overall safety data, agree on dose escalation, adjudicate individual high-grade AEs as potentially dose-limiting, and guide other major study decisions.

Efficacy Assessments:

Disease assessments will be performed based on RECIST v1.1 [REDACTED]

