1.8. Rationale for Shorter Infusion Times for Nivolumab and Ipilimumab

Long infusion times place a burden on patients and treatment centers. Establishing that nivolumab and ipilimumab can be safely administered using shorter infusion times of 30 minutes duration will diminish the burden, provided that there is no change in the safety profile. Previous clinical studies of nivolumab and ipilimumab monotherapies and the combination of nivolumab and ipilimumab have used a 60-minute infusion duration for nivolumab and a 90-minute infusion duration for ipilimumab (1-3 mg/kg dosing for both). However, both nivolumab and ipilimumab have been administered at up to 10 mg/kg with the same infusion duration (ie, 60 minutes).

Establishing that nivolumab can be safely administered using a shorter infusion time (30 minutes) is under investigation. Previous clinical studies of nivolumab monotherapy have used a 60-minute infusion duration, wherein nivolumab has been safely administered up to

In subjects who have initial radiologic evidence of PD, it is at the discretion of the investigator to continue a subject on treatment until repeat imaging is obtained. This decision should be based on the subject's overall clinical condition, including performance status, clinical symptoms, and laboratory data. Subjects may receive treatment while waiting for confirmation of PD if they are clinically stable, as defined by the following criteria:

- Absence of clinically significant signs and symptoms (including worsening of laboratory values) indicating disease progression.
- No decline in ECOG performance status.
- No requirement for intensified management of disease-related symptoms.
- Absence of rapid progression of disease.
- Absence of progressive tumor at critical anatomical sites (eg, spinal cord compression) requiring urgent alternative medical intervention.

When feasible, subjects should not be discontinued until progression is confirmed. Subjects who are deemed clinically unstable are not required to have repeat imaging for confirmation of PD and should be withdrawn from all study treatment. See additional details in Section 5.5.1.1.

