6. STUDY ASSESSMENTS

All study assessments will be performed as indicated in the schedule of clinical assessments ([Table 21](#) and [Table 23](#)), and all laboratory assessments will be performed as indicated in [Table 22](#) and [Table 24](#). [Table 25](#) presents a summary of local clinical laboratory analytes to be assessed. The order of assessments is suggested by the order of mention within the schedule. See Section [7](#) for instructions on each assessment. Further details of study procedures and assessments can be found in the Study Reference Manual.

Table 21: Schedule of Clinical Assessments – Treatment Group A (Epacadostat + Nivolumab + Ipilimumab)

Visit	Screening	Treatment Period (14-Day Cycles)				EOT	Safety Follow-Up ^b		Comments
		Cycles 1 Through 3		Cycle 4 and Beyond	Disease Status ^a		30 Days After EOT	100 Days After EOT	
		Day 1	Day 8	Day 1	See Footnote a		+ 7 Days	+ 7 Days	
Evaluation/Window	Days -28 to -1	± 3 Days	± 1 Day	± 3 Days	± 7 Days	+ 7 Days	+ 7 Days	± 7 Days	
Administrative Procedures									
Informed consent	X								
Contact IRT	X	X		X		X			
Inclusion/exclusion criteria	X	X							
Prior medical and cancer history	X								
Prior and concomitant medications	X	X	X	X		X	X	X	
Reminder card		X	X	X		X	X		
Clinical Procedures/Assessments									
Comprehensive physical examination and height	X								
Targeted physical examination		X	X ^b	X		X	X	X	
Vital signs and weight	X	X	X	X		X	X	X	
ECOG performance status	X								
Laboratory assessments	X	X	X	X		X	X		See Table 22 for required laboratory assessments.
12-Lead ECG	X	X*				X			* Cycle 1 Day 1 and Cycle 2 Day 1. See Section 7.5.4 for details.
AE assessment	X	X	X	X		X	X	X	
Tumor tissue collection	X								Only Phase 1 subjects. See Table 22 for Phase 2 fresh biopsy collection timepoints.

Table 21: Schedule of Clinical Assessments – Treatment Group A (Epcadostat + Nivolumab + Ipilimumab) (Continued)

Visit	Screening	Treatment Period (14-Day Cycles)				EOT	Safety Follow-Up ^b		Comments
		Cycles 1 Through 3		Cycle 4 and Beyond	Disease Status ^a		30 Days After EOT	100 Days After EOT	
		Day 1	Day 8	Day 1	Q8W		+ 7 Days	+ 7 Days	
Evaluation/Window	Days -28 to -1	± 3 Days	± 1 Day	± 3 Days	± 7 Days	+ 7 Days	+ 7 Days	± 7 Days	
Study Drug Administration									
Administer epacadostat in clinic		X	X						█ Epacadostat should be administered before nivolumab and ipilimumab.
Administer nivolumab		X		X					Nivolumab should be administered before ipilimumab at applicable visits.

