9.4. Statistical Analyses

Note: As Amendment 2 will serve to discontinue the study to further enrollment, limited safety and efficacy analyses will be performed. Listings will be substituted for summary tables for efficacy analyses. Summary tables will only be provided for selected safety analyses.

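### Is the ECOG condition for treating past first progression unworkable because Group A has no ECOG rating scheduled after screening?

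*Combined protocol and SAP*

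**What the plan says.** Section 5.5.1.1 states the condition: "Subjects may receive study treatment pending confirmation of PD if they are clinically stable as defined by the following criteria". Five criteria follow, one of which is "No decline in ECOG performance status". The same list appears in the Synopsis under Efficacy Assessments and in the introduction, in the text that follows Section 1.8 in the public copy. The introduction leaves the decision to the investigator and adds: "This decision should be based on the subject's overall clinical condition, including performance status, clinical symptoms, and laboratory data".

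Section 5.5.1 makes a related allowance: "A subject may continue on treatment after radiographic progression is confirmed per RECIST v1.1 if clinically stable or clinically improved". Part of that sentence is redacted.

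Section 6 says that assessments follow the schedule tables. In Table 21 (Group A) the row "ECOG performance status" has a mark at screening only. The Synopsis list of Day 1 procedures reads "targeted physical examinations, vital sign collection, collection of concomitant medications, and AE assessments will be performed", with no ECOG. Table 23 (Group B) marks ECOG at screening, at Day 1 of every cycle and at the three safety follow-up visits, but Section 4.1 reports that nobody entered Group B.

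Section 9.4 limits the analyses now that enrollment is closed: "Listings will be substituted for summary tables for efficacy analyses".

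**The concern.** A criterion about decline compares two values, and the Group A schedule supplies one. With treatment allowed for up to 2 years, the screening rating could be old by the time progression appears. The group with no subjects keeps the rating at each cycle, while the group with subjects does not, which looks like an oversight.

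Table 19 gives the criterion some weight. A clinically stable subject may continue treatment and has a repeat scan at 4 to 8 weeks. An unstable subject stops, with a repeat scan only where possible. If sites differ in whether they rate performance status at that point, or in which earlier value they compare it with, similar subjects could be handled differently. A monitor could not then check the decision against scheduled data. Amendment 2 exists largely to guide subjects who remain on treatment, and they are the ones to whom the rule applies.

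**Working it through.** The plan gives no figure to reproduce, so the check sets the passages side by side.

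**1. Is the mismatch in the current text?** Yes. The criterion stands in the Synopsis, the introduction and Section 5.5.1.1. Table 21 has no ECOG mark after screening. The blank cells are unlikely to come from reading the PDF, because the matching row of Table 23 keeps its later marks. As background only, the Amendment 2 summary in Appendix F says ECOG assessments were deleted as no longer needed, so the lean schedule was intended.

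**2. What does the criterion need?** Two values at one moment.
- The reference value exists. Inclusion criterion 11 requires ECOG 0 or 1, and Table 21 has it rated at screening.
- The current value is needed only when progression is first seen. An investigator applying Section 5.5.1.1 has to consider performance status to answer the question, and the introduction says so directly: the decision rests on "overall clinical condition, including performance status, clinical symptoms, and laboratory data". If the question arises between planned visits, Section 6.6 allows an unscheduled visit and has its assessments recorded in the eCRF.

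A rating at every cycle would give a history, but the rule does not ask for one.

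**3. Do the other criteria have their own row in Table 21?** Not all of them. Absence of rapid progression, for example, has none; it is judged from scans and the clinical picture. Table 21 still has the targeted physical examination, vital signs and weight, laboratory tests and adverse event review at Day 1 of every cycle. The stability list works as a guide to clinical judgement, not as a set of scheduled measurements.

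**4. Does the confirmatory scan depend on the ECOG result?** Only loosely. The imaging comment in Table 21 asks for a scan 4 to 8 weeks after progression without mentioning stability. The Synopsis names investigator discretion among the reasons a follow-up scan may not have been done.

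**5. Does Section 5.5.1 depend on ECOG?** It refers to subjects who are stable or improved, is permissive, points to Section 5.5.1.1 and does not name ECOG. With part of the sentence redacted, it cannot be treated as the same test.

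**6. Can a result change?** Section 9.4.1 defines response rate, progression-free survival and duration of response without ECOG. Where no follow-up scan is made, Section 5.5.1.1 dates progression at the first unconfirmed finding. Stopping or continuing could alter which later scans exist, and so whether a response after unconfirmed progression is recorded under the i-prefixed categories of Section 5.5.1.1. By then the RECIST v1.1 progression date is already fixed. Sample size, power and the 1-sided 5% level do not involve ECOG.

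**The case for a change.** The strongest reply is that an investigator being able to rate ECOG is not the same as being required to. No text orders a rating on the day progression is seen, so its recording is left to each site. A protocol that names a condition for continued treatment should, on this view, schedule what is needed to check it. The deliberate removal of ECOG from the schedule makes the retained criterion look more like a missed edit.

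The part about verification stands: a decline cannot be confirmed from protocol-scheduled data in Group A, and the stability wording and the schedule do not match.

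The claim that sites will therefore diverge in a way that matters does not stand. Table 19 makes continuation for stable subjects a matter of investigator discretion, so some variation is built in and a scheduled rating would not remove it. The contrast with Table 23 also says less than it seems to. Of its six marked columns, one is screening and three are post-treatment follow-up, which leaves two on-treatment columns, in a group with no subjects.

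**Conclusion.** The mismatch is real but clerical, and no change to the design or analysis follows. Investigators following the plan as written would consider performance status at the one decision where it counts and compare it with the screening value. What is lost is a scheduled record of that comparison, in a study closed to enrollment, with treatment capped at 2 years and efficacy reported as listings. The effect on the RECIST v1.1 response rate, progression-free survival and duration of response definitions, and on power and alpha, is nil.

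This rests on two assumptions: that investigators read the criterion as a judgement made when progression appears, as the introduction implies, and that the efficacy listings are not later used for formal inference. The documents do not say how many Group A subjects were still on treatment under Amendment 2. Some may also have on-treatment ratings from before it. Neither unknown alters the conclusion.

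The stability criteria in the Synopsis, the introduction and Section 5.5.1.1 should be reconciled with Table 21 as housekeeping when the text is next opened. Which of them moves is a clinical choice for the sponsor, on which this review takes no view.
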